# 3.7 Key Data Items

#### Study Analysis Population Definition:

- Intended-To-Treat (ITT) population: All subjects who are randomized into the study.
- Per-Protocol (PP) population: All ITT subjects without any major protocol violations.
- Safety Population: All ITT subjects who receive at least one dose of study drug.

#### **Important Derived Variables:**

- Age = (Screening Date Date of Birth +1)/365.25.
- Prior Medications and Treatments: the medications and treatments started before the subject was enrolled to the study without any change after enrollment.
- Concomitant Medication and Treatments: the medications and treatments started after the subject was enrolled to the study. Any medications and treatments started before enrollment but changed after enrollment will be considered as concomitant medications and treatments.
- Baseline: All clinical measurements (safety and efficacy data) collected at Day 1 or before the first dose will be analyzed as baseline. One baseline is for both blinded phase and open-label phase.
- Post Baseline: All clinical measurements (safety and efficacy data) collected after the first dose will be analyzed as post baseline. For blinded phase, the scheduled post-baseline visits are at Week 13, 26, 39 and 52. For open-label phase, the scheduled post-baseline visits are at Week 65, 78, 91 and 104.
- Study Drug Compliance by Visit

 $\frac{\text{Weight (g) of dispensed canisters} - \text{Weight (g) of returned canisters}}{3.52\text{g} \times \text{ number of days between visits}} \times 100\%,$ 

- The number of days between visits = the date of current visit the date of last visit +1
- $\circ\,$  Drug compliance will be calculated only for the subjects who returned all canisters dispensed.
- Overall study drug compliance of the study phase will be the average of visit compliance
- Treatment emergent Adverse Events (TEAE): Any AEs started on or after the day of the first study drug dosed.

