## 6.0 TREATMENT OF SUBJECTS

Investigational product will only be shipped to Investigators who have provided BHR PHARMA, LLC (or an authorized representative) all required study documents, including Institutional Review Board (IRB) approval, have executed a clinical trial agreement (CTA), and have been approved by BHR PHARMA, LLC to begin the study. Study drug will be provided by BHR PHARMA, LLC (or authorized representative) as blind-labeled ready-to-use canisters containing 4-OHT gel or placebo.

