# • Study Week 45: Telephone Call (+/- 2 weeks)

During this visit, the site will call the subject and review the subject's dosing compliance, product application, and query for any AEs.

• Study Week 52: (+/- 2 weeks) – End of Blinded Phase and End of Study Visit

Subjects will return to the clinic for study assessments. A Physical Examination including a breast exam will be performed, vital signs, height and weight will be measured and AEs and the use of any concomitant medications will be recorded. Laboratory measurements will be performed and will include hematology, blood chemistry, coagulation factors, hormones and bone biomarkers. PK measurements of 4-OHT isomers E and Z will be taken. A urine pregnancy test will be performed on women of child bearing potential. Treatment canisters will be weighed and the diary checked for study compliance. A mammogram will be performed.

Subjects will be offered the opportunity to participate in the Open-Label-Extension Phase of the study. Informed consent will be obtained from those subjects choosing to continue in the Open-Label-Extension Phase. Open-labeled study drug will be dispensed to those subjects who have agreed to administer the BHR-700 gel for an additional 52 weeks.

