#### 1.2 Design

This is a multi-center, randomized, double-blind, placebo-controlled study in women identified as having dense breast tissue upon screening mammography.

Subjects who give informed consent will have screening evaluations, including hormone measures of FSH, Estradiol and Estrone to determine menopausal state. Those subjects meeting entry criteria, will be stratified, based on their hormone levels, into pre/peri and post menopause groups and randomized within those groups 2:1 to receive either 8 mg/day (4 mg/breast) BHR-700 gel or placebo for up to 52 weeks. At the Principal Investigator's (PI) discretion, subjects may be allowed to reduce the dose to 4 mg/day (2 mg/breast) in cases of intolerance.

Subjects will apply the gel to both breasts once per day. The first dose will be applied under the supervision of the PI/designee. Subsequent doses will be self-administered daily by the subject until she has completed 52 weeks of study drug administration. Study drug compliance will be checked at each study visit. Subjects will be asked to capture daily gel administration in a diary and drug canisters will be weighed on release to the subject and on return. The canister weight will be recorded in grams. If the study drug is discontinued or interrupted, the reason(s) will be recorded. During treatment period, subjects will be evaluated at Day 1 and every 13 weeks (±2 weeks) thereafter.

A planned sample size of 330 women, identified as having dense breast tissue upon screening mammography, will be randomized to receive either BHR-700 gel or placebo (at 2:1 ratio). Considering an attrition rate of approximately 15%, it is expected to have 272 evaluable women (4-OHT: 181 & Placebo: 91) who will have both baseline and 52 week measurements of percent mammographic density (MD) of the breast.

Subjects who complete the double-blind phase of the study will be offered entry into an open-label follow-up period for an additional 52 weeks.

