#### Laboratory Tests

• Laboratory data (haematology and blood chemistry) will be summarized for baseline, post baseline, and change from baseline.

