# 5.1.2 Summary of safety endpoints

29. Table [TAE01b] Summary of Adverse Events (Open-Label Phase) – Safety Population

- 30. Table [TAE02b] Number (%) of Subjects with Adverse Events by Body System and Preferred Term (Open-Label Phase) Safety Population
- 31. Table [TAE03b] Number (%) of Subjects with Serious Adverse Events by Body System and Preferred Term (Open-Label Phase) Safety Population
- 32. Table [TAE04b] Number (%) of Subjects with Severe Adverse Events by Body System and Preferred Term (Open-Label Phase) Safety Population
- 33. Table [TAE05b] Number (%) of Subjects with Study Agent Related Adverse Events by Body System and Preferred Term (Open-Label Phase) Safety Population
- 34. Table [TAE06b] Number (%) of Subjects with Adverse Events by Preferred Term and Overall Frequency (Open-Label Phase) Safety Population
- 35. Table [TVS01b] Summary of Vital Signs and Change from Baseline (Open-Label Phase) Safety Population
- 36. Table [TPE01b] Summary of Physical Examination (Open-Label Phase) Safety Population
- 37. Table [TLB01b] Summary of Laboratory (Hematology) Test Results (Open-Label Phase) Safety Population
- 38. Table [TLB02b] Summary of Laboratory (Blood Chemistry) Test Results (Open-Label Phase) Safety Population
- 39. Table [TLB03b] Summary of Urine Pregnancy Test Results (Open-Label Phase) Safety Population

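### One Day 1 baseline for both phases puts the placebo year into the open-label change from baseline of women randomised to placebo (minor)

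*SAP*

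**What the plan says.** SAP 3.7, under Important Derived Variables, states that measurements "collected at Day 1 or before the first dose will be analyzed as baseline", for safety and efficacy data alike, and then: "One baseline is for both blinded phase and open-label phase". The open-label post-baseline visits it names are Weeks 65, 78, 91 and 104.

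Study drug includes placebo. Protocol 6.0 describes it as "blind-labeled ready-to-use canisters containing 4-OHT gel or placebo". For a woman randomised to placebo, the first dose is therefore placebo on Day 1.

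Both arms can roll over. SAP 1.2: "Subjects who complete the double-blind phase of the study will be offered entry into an open-label follow-up period". All who enter then receive active gel. Protocol 7.3, Week 52 visit: "Open-labeled study drug will be dispensed to those subjects who have agreed to administer the BHR-700 gel for an additional 52 weeks".

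Three planned open-label tables are affected (SAP 5.1.2):

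- TVS01b, titled "Summary of Vital Signs and Change from Baseline (Open-Label Phase) Safety Population".
- TLB01b (hematology) and TLB02b (blood chemistry). Their titles do not mention change, but SAP 3.3.1 says that laboratory data "will be summarized for baseline, post baseline, and change from baseline", without limiting this to one phase. Blood chemistry includes the lipids (SAP 3.7). Lipid change is a secondary endpoint, and SAP 2.2.2 applies the secondary endpoints to both phases.

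**The concern.** An open-label change-from-baseline table invites the reader to see what happened to women while they took the open-label drug. For women randomised to BHR-700, a Day 1 baseline serves that purpose: it precedes all exposure, and the change covers up to 104 weeks on drug. For women randomised to placebo it does not. Their last value before any 4-OHT is the Week 52 value, but the SAP measures from a year before that.

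What is at stake is attribution in descriptive safety tables. After early termination the report concentrates on safety and PK/PD (SAP 3.8), so these tables are a fair part of what it will show for the second year.

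**Working it through.** The plan gives no figure on this point to reproduce. The check sets the baseline rule beside the visit schedule and the planned outputs.

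**Step 1: what the open-label change contains.** For a woman randomised to placebo, let D be her change from Day 1 to Week 52 (on placebo) and E her change from Week 52 to an open-label visit (on BHR-700). Under SAP 3.7 the tabulated value is D + E. Measured from the last value before the first open-label dose, it would be E.

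**Step 2: share of the interval spent on placebo.** The formula is 52 / w, with w the nominal visit week. The Week 52 visit has a window of 2 weeks either side, so these are nominal.

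| Visit (week) | Weeks on drug, w − 52 | Share on placebo, 52 / w | Planned measures |
|---|---|---|---|
| 65 | 13 | 52/65 = 80% | vital signs |
| 78 | 26 | 52/78 = 67% | vital signs, laboratory |
| 91 | 39 | 52/91 = 57% | vital signs |
| 104 | 52 | 52/104 = 50% | vital signs, laboratory |

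The last column follows Protocol 8.5 and 8.7. The laboratory tables are affected only at Weeks 78 and 104.

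**Step 3: from time to distortion.** The share of the tabulated mean change that belongs to the placebo year is D / (D + E). It is zero if D is zero, however long the placebo year was. The documents give no D for vital signs, hematology or chemistry, so no size can be stated for the three tables.

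The only placebo-year change in the plan is for breast density: SAP 2.3 assumes reductions of 2% on placebo and 6% on active. As an illustration only, assume that changes add and that the drug year brings 6%. The Week 104 change is then 2 + 6 = 8% from Day 1 and 6% from Week 52, and the placebo share is 2/8 = 25%. With D from 0 to 4%, the share runs from 0/6 = 0% to 4/10 = 40%. No open-label density table is planned, so this would matter only for an ad hoc density analysis that adopted the same baseline.

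**Step 4: if the arms are pooled.** Allocation is 2:1. If roll-over is equal in both arms (an assumption; the documents give no roll-over figures), about 1/3 of open-label women come from placebo. A pooled Week 104 mean would then carry D/3 from the placebo year. It would also mix women with a nominal 104 and 52 weeks on drug.

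**Step 5: does other text remove the problem?** SAP 3.1 says that summaries are by treatment group and time point. It does not say whether treatment group in the open-label phase means the original arm. No section sets a second baseline. Vital signs and laboratory tests are already scheduled at Week 52 (Protocol 7.3, 8.5, 8.7 and Appendix 1), so the pre-drug values exist.

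**The case against.** The case for leaving the rule alone has several parts.

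- **A single baseline is a declared choice.** It is transparent and suits the larger arm. This stands, and is why the Day 1 change should stay.
- **The data are not lost.** Subject listings of vital signs and laboratory results are planned for both phases (SAP 4.2.2 and 5.2.2), so change from Week 52 can be derived by hand. This stands, and lowers the severity. Subtracting published means is a poorer substitute: the blinded-phase mean includes women who did not roll over, and subtraction gives no standard deviation for E.
- **The consequence is narrow.** Three descriptive tables are affected, with no planned test. The primary endpoint is blinded phase only (SAP 2.2.1), PK/PD is reported for the blinded phase only (SAP 3.8), and no efficacy analysis is planned (SAP 3.3.2). All of this stands.

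Stronger readings that a reader might infer are not supported:

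- **That no planned table shows change since first exposure.** The shells are an attachment whose content is not available, so the most that can be said is that the SAP text specifies none. A split by original arm in the shells would help, but would not by itself take the placebo year out of the change.
- **That women randomised to placebo offer the only within-woman comparison off and on drug.** Women randomised to BHR-700 also have pre-dose values followed by on-drug values, with a concurrent randomised control. What is particular to the placebo arm is the switch from placebo to drug in the same woman.
- **That 50% to 80% is the size of a bias.** These are shares of calendar time.
- **That a Week 52 baseline would isolate the drug effect.** After Week 52 nobody is on placebo, so change from Week 52 still mixes drug with ageing, menopausal transition and regression to the mean.

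**Conclusion.** The point holds, at minor severity. Under the stated rule, open-label change for women randomised to placebo spans a nominal 52 weeks on placebo as well as the time on drug, in TVS01b, TLB01b and TLB02b. The mechanism follows from the definitions and needs no assumption beyond the nominal visit schedule. The size of any distortion is unknown, because it depends on placebo-year drift in vital signs and laboratory values that the documents do not give; it could be nil. The estimate that about one third of open-label women are affected assumes equal roll-over. How many women randomised to placebo reached Week 78 or Week 104 before the study ended is not stated.

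**What to change.** In SAP 3.7, keep the Day 1 baseline and its change for all women. For women randomised to placebo, add a second reference value, the last measurement before the first open-label dose, and report change from it in TVS01b, TLB01b and TLB02b. Define it by date relative to that dose and not by the visit label, since SAP 3.8 merges Week 52 and End of Study under one nominal visit. State that these three tables are shown by original randomised arm. A footnote should say that change from the pre-drug value is uncontrolled, because there is no concurrent placebo group after Week 52. Any ad hoc open-label density analysis should follow the same rule.

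The cost is one derived flag and extra columns, with no new data collection. The downside is longer tables.

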#### 3.2 Subject Disposition, Demographics, Baseline Characters and Study Drug Compliance

- Subject disposition will be summarized for all enrolled subjects.
- Demographics and baseline characters will be summarized on ITT population using descriptive statistics.
- General medical history, breast cancer history, menstrual history and concomitant medications data will be summarized on ITT population.
- Study drug compliance will be summarized by visit using descriptive statistics. The compliance (%) is defined as the percentage of drug administrated as planned dose, which will be calculated as below

 $\frac{\text{Weight (g)of dispensed canisters} - \text{Weight (g)of returned canisters}}{3.52g \times \text{ number of days of treatment period}} \times 100\%$ 

The expected weight of daily dose is based on BHR "Rule of Thumb" guidance below.

- 4 squirts is an 8 mg/day dose.
- Each squirt is supposed to be 1 mL.
- 1 mL of gel = 0.88 g (based on the density of the gel: 0.88g/mL).
- 4 squirts (mL)×0.88 g/mL = 3.52 g expected in a normal 8mg/day dose day.

Sections 4.1.1 and 4.2.1 list the planned summary tables and data listings for blinded phase. Sections 5.1.1 and 5.2.2 list the planned summary tables and data listings for open-label phase.

Drug compliance will be calculated only for the subjects who returned all canisters dispensed. Drug compliance will be set as missing for the subjects who didn't return all canisters dispensed.

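### The SAP's compliance denominator adds a day to every visit interval, so interior visit days are counted twice and full adherence over four full intervals averages about 99%, not 100%

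*SAP*

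**What the plan says.** SAP 3.7 (Important Derived Variables) defines compliance by visit as the weight of gel used divided by 3.52 g times the number of days between visits. That number is the current visit date minus the last visit date plus one day ("the date of last visit +1"), and the rule applies to every interval. For the phase, "Overall study drug compliance of the study phase will be the average of visit compliance".

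The interval boundaries are also in 3.7: "For blinded phase, the scheduled post-baseline visits are at Week 13, 26, 39 and 52". SAP 1.2 gives the window: "subjects will be evaluated at Day 1 and every 13 weeks (±2 weeks) thereafter". The same section sets the dosing frequency: "Subjects will apply the gel to both breasts once per day".

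SAP 3.2 derives the daily weight ("3.52 g expected in a normal 8mg/day dose day"). Its own version of the compliance formula has a different denominator, the "number of days of treatment period", with no added day stated. Both sections set compliance to missing for a woman who did not return all her canisters.

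**The concern.** Adding one day is correct for a single period counted inclusively. It is not correct for consecutive periods that share a boundary date. The Week 13 visit day closes one interval and opens the next, and the same holds at Weeks 26 and 39. Each of those days has one application, drawn from one set of canisters, but the rule expects a dose from both sets.

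What is at stake is the accuracy of a reported figure: compliance by visit in Table TSD01a and Listing LSD01a, and in LSD01b for the open-label phase. One extra day weighs more in a short interval, and the unweighted average gives a short interval the same weight as a 13-week one. SAP 1.3 says early termination shortened treatment for a large proportion of subjects, and SAP 3.8 places end-of-study visits under the Week 52 label, so short last intervals are plausible. A shortfall produced by the formula would then read as missed doses.

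**Working it through.** **Daily weight.** SAP 3.2 gives four presses of 1 mL, with the conversion "based on the density of the gel: 0.88g/mL". 4 × 0.88 = 3.52 g, so the SAP's figure is reproduced. At nominal delivery it cancels, and compliance becomes doses used divided by days counted.

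**Day count.** Put the visits on study days 1, 92, 183, 274 and 365.
- Each denominator: 91 + 1 = 92 days.
- Sum: 4 × 92 = 368.
- Calendar days from Day 1 through Week 52: 365.
- Excess: 3 days, which are the Week 13, 26 and 39 visit days.

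**Full adherence, four 91-day intervals.**
- Visit-day doses from the new canisters, none on the Week 52 day: 91/92 = 98.9% in each interval, so the mean is 98.9%.
- Visit-day doses from the old canisters: the first interval holds 92 doses and scores 100%, and the other three score 98.9%. Mean (100 + 3 × 98.91)/4 = 99.2%.
- Visit-day doses from the new canisters, plus a final-day dose from the last kit: the last interval scores 100%. The mean is again 99.2%.

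Because the four denominators are equal, the mean is total doses divided by 368. That is 364/368 = 98.9% or 365/368 = 99.2%, whichever canisters are used at the interior visits. With visits at the limits of the two-week window, the phase mean runs from about 98.8% to 99.3%.

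**Short last interval.** A d-day interval with d doses scores d/(d + 1): 28/29 = 96.6% and 14/15 = 93.3%. The documents give no actual interval lengths, so these are assumptions. For 91 + 91 + 14 days with no missed dose:
- New canisters on visit days, no final-day dose: (98.91 + 98.91 + 93.33)/3 = 97.1%.
- Old canisters on visit days: (100 + 98.91 + 93.33)/3 = 97.4%.
- New canisters on visit days, final-day dose taken: (98.91 + 98.91 + 100)/3 = 99.3%.

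**Single interval.** A woman dosed on Day 1 who also doses from the same kit on her only follow-up visit day has d + 1 doses in d + 1 counted days, which is 100%. Here the added day is right.

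**Dropping the added day everywhere.** The denominators sum to 4 × 91 = 364, one short of 365. With old canisters used on visit days, the first interval becomes 92/91 = 101.1% and the phase mean (101.1 + 3 × 100)/4 = 100.3%.

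**The case against.** The best case against making much of this has four parts.

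- **Priming and delivery.** Protocol 6.5 requires each canister to be primed by pressing until gel appears and then three more times. At 0.88 g per press, four presses are 3.52 g, one whole day's dose. No passage says whether the release weight is taken before or after priming. One canister primed after weighing brings a 91-dose interval to (91 + 1)/92 = 100%. All six canisters of a kit (Protocol 7.2) would give (91 + 6)/92 = 105.4%. Delivery 1.1% above nominal (0.88 × 92/91 = 0.890 g per press) has the same effect as one such canister. So a reader might infer that no fully adherent woman can score 100%, but the documents do not support that. It is true only at nominal delivery with priming gel outside the weights. This part stands as a limit, although an uncontrolled error in the other direction does not make the day count right.
- **Who is affected.** A reader might also infer that every visit day is double-counted and every woman is scored low. Within the blinded phase, Day 1 and the final visit are counted once, a single-interval woman may be scored correctly, and some women have no compliance value at all.
- **Size for short intervals.** A reader might take a loss of about 7 points in a two-week last interval as the expected effect. That needs an assumed interval length and no dose from the last kit on the final day. If that dose is taken and the interval opened with a new-canister dose, the interval scores 15/15 = 100%.
- **Consequence.** Compliance is summarised descriptively, no threshold is set, the per-protocol definition does not mention it, and the rule is the same in both arms. This stands and keeps the point minor.

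None of this answers the core: three interior days are counted twice, and nothing elsewhere in the SAP corrects it.

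**Conclusion.** The rule is wrong as written for any woman with more than one interval, because each interior visit day enters two denominators. For four full intervals the fully adherent average is understated by about 0.8 to 1.1 percentage points. For the assumed 91 + 91 + 14 days the understatement is about 0.7 to 2.9 points. These sizes rest on 3.52 g per day, a release weight that excludes priming gel, and all canisters returned. The net error in an individual woman's reported figure is not known, because the order of weighing and priming is not stated. The point affects a descriptive table and its listings, and no test or population definition.

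**What to change.** Count each dosing day once in SAP 3.7. Use current visit date minus previous visit date for all intervals except the one end interval that holds the extra dose, and keep the added day there. That is the first interval if visit-day doses come from the old canisters. It is the last if they come from the new canisters and a final-day dose is taken. If neither applies, no interval needs the extra day. The SAP should state which convention it assumes.

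Alternatively, compute overall compliance as total grams used divided by 3.52 g times the distinct treatment days, in line with the SAP 3.2 denominator. This does not depend on which canisters supplied the visit-day doses, and it stops a short interval from weighing as much as a full one. The text should say whether the final visit day counts as a treatment day. Either way, 3.2 and 3.7 should use the same denominator.

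The cost is one SAP line and one line of code. Reported compliance rises slightly.
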